A factorial design will be used to compare porosity of sponge 25 mm 10 pores per inch (PPI) vs. 25 mm 20 PPI, and Barrett's Esophagus vs. normal esophagus. Tolerability will be measured using a tolerability score as well as level of mucosal abrasion (scale 0-6, 6=worst). The assumed standard deviation for the tolerability score of 2.2 was obtained from Sami, et al.. Using a two-sided test of significance of 5% and 80% power, we can detect a minimal shift in tolerability score of at least 2. For mucosal abrasion score, a rough estimate of 1 standard deviation (s.d. ≈ range of data / 4) will be used and assuming a two-sided test of significance of 5% we have 86% power to detect a difference in mean mucosal abrasion score of at least 1. DNA yield will be measured using wild type Beta-actin. Using a two-sided test of significance of 5% we have 82% power to detect a fold change difference of 50%. All above power calculations are based on detection of main effect comparisons with n=20 per group. The ability to detect interactions between main effects will be very limited with the given sample size. Recruitment will continue until 40 individuals have successfully completed the sponge procedure using the

25 mm sponge. We anticipate 25% will decline swallowing sponges after they have consented, therefore the total number of people we anticipate recruiting will be set at 60.

Phase 2: For the detection of Barrett's Esophagus, sample size justification will be based on minimizing the width of the 95% confidence interval of the sensitivity for detecting Barrett's Esophagus with a fixed specificity of 90%. From table 2 below, based on various assumed sensitivities, the largest confidence interval width for the proposed sample size is less than ±9%. Similarly for detection of dysplasia among Barrett's Esophagus patients, the largest width for the proposed sample size is less than ±12. These confidence widths are reasonable for this initial feasibility study. We also intend to perform multivariable modeling using machine learning techniques to evaluate a minimum of 14 methylation markers. Using the rule of thumb for machine learning of 10-15 events per marker, a minimum of 140 to 210 cases and an equal number of controls is required (total 280 to 420 patients) to account for assay failures and indeterminate histological findings on endoscopic exam. We anticipate enrolling up to 1000 participants.

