In addition, clinically archived FFPE tissue from up to 10 cases will be used to assess methylated DNA marker levels in biopsies versus the sponge.

Due to the known dysplasia miss rate with routine surveillance endoscopy, we hypothesize that there will be undetected or missed dysplasia in BE patients with a negative surveillance histology. This imperfection in the endoscopic "gold" standard will bias the resulting accuracy estimates of methylation markers in a multitude of ways. There are several approaches in the literature to address this issue; all with their own caveats. The three approaches that will be investigated are latent class analysis, Bayesian estimation, and discrepant resolution. We have hence inflated the sample size estimates in table 2 to correspond with a 30% prevalence of undetected dysplasia in those with no dysplasia on conventional surveillance endoscopy to ensure that we have 50 true BE subjects without dysplasia.

Table 2

	BE vs. No BE			BE no dysplasia vs. BE w/dysplasia				
Confidence Level	0.95	0.95	0.95	0.95	0.95	0.95	0.95	0.95
Sensitivity	0.75	0.80	0.85	0.90	0.75	0.80	0.85	0.90
Confidence bands	0.085	0.078	0.070	0.059	0.105	0.097	0.087	0.073
N no BE/BE without dys/BE with dys	100	100	100	100	65	65	65	65

Statistical analysis

Phase 1: Tolerability score and level of mucosal abrasion will be summarized as median and interquartile range. Analysis of variance will be used to detect statistically significant differences in tolerability score and level of mucosal abrasion between different levels of sponge porosity and size. Failure/complication rate will be summarized as the percentage of the group total. Comparisons between sponge porosity and size for failure/complication rate will be analyzed using the Chi-squared test.

Phase 1 and 2: Marker specificity will be defined as the 90th percentile value in subjects without BE. Several markers will be combined based on the coefficients from a logistic regression model using subjects with BE vs subjects without BE as the response. This approach is used as they represent the broadest spectrum of disease and any marker combination that fails to discriminate between these two subgroups would not be of future value. The specificity of the combined markers will then be set equal to the 90th percentile in non-BE subjects. The corresponding sensitivity of individual markers as well as combined markers will be estimated with 95% confidence intervals.

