Marker specificity will be defined as the 90th percentile value in subjects with BE and no dysplasia. Several markers will be combined based on the coefficients from a logistic regression model using BE subjects with dysplasia vs subjects without dysplasia as the response. This approach is used as they represent the broadest spectrum of disease and any marker combination that fails to discriminate between these two subgroups would not be of future value. The specificity of the combined markers will then be set equal to the 90th percentile in BE subjects without dysplasia. The corresponding sensitivity of individual markers as well as combined markers will be estimated with 95% confidence intervals.

The association of demographic (age, gender, race), anthropometric (body mass index, waist hip ratio) and circulating biomarker levels (leptin, interleukins) with a BE diagnosis will be assessed using univariate and multivariable logistic regression analysis.

References:

- 5. Fitzgerald RC, di Pietro M, Ragunath K, et al. British Society of Gastroenterology guidelines on the diagnosis and management of Barrett's oesophagus. Gut 2014;63:7-42.
- 9. Phoa KN, van Vilsteren FG, Weusten BL, et al. Radiofrequency ablation vs endoscopic surveillance for patients with Barrett esophagus and low-grade dysplasia: a randomized clinical trial. JAMA 2014;311:1209-17.

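### The plan sets a minimum of 140 to 210 cases for its 14-marker modelling, but proposes only 100 and 65 per group and gives no number that shows the minimum is met for dysplasia

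*Combined protocol and SAP*

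**What the plan says.** The Phase 2 paragraph of the section Sample size and Statistical analysis gives two justifications in turn.

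- **Precision.** The size is based on "minimizing the width of the 95% confidence interval of the sensitivity for detecting Barrett's Esophagus with a fixed specificity of 90" percent. Table 2 supplies the half-widths. Its size row, labelled "N no BE/BE without dys/BE with dys", shows 100 under BE against no BE and 65 under the dysplasia comparison. The text bounds the BE interval at under ±9% and says of dysplasia that "the largest width for the proposed sample size is less than ±12".
- **Modelling.** At least 14 markers are to be evaluated by machine learning, at 10 to 15 events per marker, so "a minimum of 140 to 210 cases and an equal number of controls is required". The total is given as 280 to 420. The paragraph ends: "We anticipate enrolling up to 1000 participants".

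The Statistical analysis text for Phases 1 and 2 then describes two separate marker combinations. One separates BE from no BE. The other is a logistic model "using BE subjects with dysplasia vs subjects without dysplasia as the response". In each, the cut-off is the 90th percentile of the comparison group, and the sensitivity at that cut-off is reported. The Phase 2 aims list dysplasia detection as an aim of its own.

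**The concern.** The plan calls 140 to 210 cases a minimum, yet the sizes it describes as proposed are all smaller. The gap is widest for dysplasia, where the events are patients with BE and dysplasia. The only planned number for that group anywhere in the plan is the 65 in Table 2. The text does not say whether the cases in the modelling rule are BE patients or dysplasia patients, and nothing divides the 1000 among no BE, BE without dysplasia and BE with dysplasia.

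What is at stake is the dysplasia result. If many coefficients are estimated from few events, and the cut-off is taken from the same patients, the reported sensitivity is too high and the specificity of 90% is not what new patients would see. The Statistical analysis text describes neither shrinkage nor validation that would correct for this.

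**Working it through.** **Inputs from the plan.** At least 14 markers; 10 to 15 events per marker; minimum of 140 to 210 per group; Table 2 sizes of 100 and 65; ceiling of 1000; assumed sensitivities from 0.75 to 0.90.

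**1. Reproduce the plan's own figures.**

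Modelling minimum: 14 × 10 = 140 and 14 × 15 = 210; doubled, 280 and 420. These agree with the text.

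Table 2 half-widths, from 1.96 × √(p(1 − p)/n):

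| Sensitivity p | 0.75 | 0.80 | 0.85 | 0.90 |
|---|---|---|---|---|
| n = 100 | 0.085 | 0.078 | 0.070 | 0.059 |
| n = 65 | 0.105 | 0.097 | 0.087 | 0.073 |

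All eight match the row "Confidence bands 0.085 0.078 0.070 0.059 0.105 0.097 0.087 0.073". This also confirms that the size row is to be read as 100 for the first four columns and 65 for the last four.

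**2. Events per marker at the proposed sizes.**

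- Dysplasia comparison: 65/14 = 4.6.
- BE against no BE: 100/14 = 7.1.
- If the two BE groups are pooled for the BE model: (65 + 65)/14 = 130/14 = 9.3.

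All are below 10. Conversely, 65 dysplasia cases support 65/15 = 4.3 to 65/10 = 6.5 markers, that is 4 to 6.

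**3. What the ceiling of 1000 would have to contain.** For the dysplasia model to meet the rule, 140/1000 = 14% to 210/1000 = 21% of participants would need dysplasia, with as many again having BE without it. The plan intends to enrich for BE and dysplasia (Participants) but gives no quota or expected fraction, so this can be neither confirmed nor ruled out.

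**4. What overfitting could cost.** This is a simulation under assumptions that are not in the plan: independent normal markers, 3 informative with a 1 SD shift and the rest noise; an unpenalised logistic fit; the cut-off at the 90th percentile of the same controls; at least 600 replicates per setting; performance in new patients computed from the known distribution.

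| Markers | Per group | Apparent sensitivity at nominal 90% specificity | Sensitivity in new patients | Specificity in new patients |
|---|---|---|---|---|
| 14 | 65 | 0.76 to 0.77 | 0.70 to 0.71 | 83% |
| 14 | 140 | 0.71 to 0.72 | 0.69 | 87% |
| 5 | 65 | 0.71 | 0.69 to 0.70 | 87% |

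Ranges reflect repeat runs. At 65 per group with 14 markers, sensitivity is overstated by about 6 points and the false-positive rate is about 17% instead of 10%. With 5 markers the overstatement is 2 points or less.

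**The case against.** The strongest reply is that Table 2 is a precision calculation and not an enrolment target. The modelling requirement is stated separately and is larger, and the ceiling of 1000 is well above 280 to 420. Nothing says that the dysplasia model will be fitted on 65 against 65. The logistic analyses combine an unspecified few markers; the figure of 14 belongs to the machine-learning evaluation, for which no algorithm is named. The preliminary dysplasia panel had 3 markers, and the plan describes itself as an initial feasibility study.

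Much of this stands, and it limits what may be concluded. Four stronger readings are tempting, and the documents do not support them.

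- *The study will miss its minimum.* The plan leaves this open. A missing allocation shows that the minimum is not secured, not that it fails.
- *The ±9% and ±12 bounds are wrong.* Both are true at Table 2's sizes: 8.5% is below 9%, and 10.5% is below 12%. The second is merely loose. It equals the value at n = 50 (1.96 × √(0.75 × 0.25/50) = 12.0%), and 50 is the target that the text names before its inflation for undetected dysplasia.
- *Table 2 errs by using 100 where 130 BE patients are implied.* That choice is conservative: 130 would give ±7.4%.
- *A specificity of 83% is to be expected.* It needs both 65 against 65 and all 14 markers in one unpenalised logistic model, and the plan commits to neither. The 140-per-group row also shows that meeting the rule still leaves specificity at 87%. That remainder comes from setting the cut-off in the same patients, which is a validation question and separate from group sizes.

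The reply does not supply a dysplasia number. A ceiling on total enrolment cannot stand in for one when dysplasia is the event in a model of its own.

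**Conclusion.** The point holds as a failure to reconcile two parts of the sample size section. The plan's stated minimum is 140 to 210 per group, its proposed sizes are 100 and 65, and nothing in between shows that the minimum is met for dysplasia. At the sizes given, the events per marker are 4.6 for dysplasia and 7.1 for BE (9.3 with BE pooled), against 10 to 15. The BE model may well be covered by enrolment toward 1000; the dysplasia model is the one left exposed.

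The arithmetic is certain. The size of the bias is conditional: about 6 points of sensitivity and 7 points of specificity at 65 per group with 14 markers, and about 2 and 3 points with 5 markers, under the marker distribution assumed above. The direction follows from fitting and thresholding on the same patients; the amounts would change with other effect sizes or correlated markers. The precision statements need no correction.

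**What to change.** 1. State a planned number for each of no BE, BE without dysplasia and BE with dysplasia. Say which comparison the minimum of 140 to 210 covers, and recompute Table 2 and its text from those numbers. For reference, the largest half-width (sensitivity 0.75) is ±10.5% at 65, ±7.4% at 130, ±7.2% at 140 and ±5.9% at 210. If 65 stays, tighten ±12 to ±10.5% as a minor edit.
2. Before the dysplasia model is fitted, pre-specify that its number of markers may not exceed the dysplasia cases obtained divided by 10 to 15. At 65 cases that is 4 to 6 markers, starting from the preliminary 3-marker set. Alternatively, specify a penalised fit.
3. Only if the planned dysplasia number stays near 65 should the plan say that the rule is not met for that comparison.

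The cost is restated figures and analysis wording, with no extra patients. The downside is that fewer markers, or shrunken coefficients, enter the dysplasia model if dysplasia cases are few.

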- v. Endoscopic brushings will be obtained from the Barrett's mucosa in BE cases, and from the squamous mucosa in control subjects. Brushings will be obtained using a high capacity cytology brush (Hobbs Medical) to enable detection of methylation biomarkers of dysplasia. 1 brush will be used for every 5 cm of Barrett's epithelium in BE case subjects. In control subjects, 1 brush will be used to sample the cardia and the distal 5cm of the esophageal squamous mucosa. These brushings will be stored at -80°C for identification of additional biomarkers.
- vi. Two research biopsies will be obtained from the gastroesophageal junction in controls for identification of methylated DNA biomarkers from the GEJ. One will be frozen and stored at -80°C and one will be formalin fixed, paraffin embedded.
- vii. The diagnostic part of the procedure will be video recorded and stored in a deidentified fashion for subsequent review.
- viii. Patients who are biomarker positive (for dysplasia related DNA methylation markers) but negative for dysplasia, as well as those biomarker negative but positive for dysplasia on clinical surveillance histology will be offered a research endoscopy (funded by the study) after biomarker analysis is complete, for additional endoscopic surveillance to detect prevalent dysplasia which may have been missed at the initial study endoscopy as well as assess for sensitivity of the marker panel. In addition to surveillance biopsies (paid for by the study), sponge procedure will be repeated and research esophageal brushings using a high capacity endoscopic brush (Hobbs Medical) will be obtained for detection of methylated biomarkers of dysplasia.
- ix. An equal number of biomarker negative (for dysplasia related DNA methylation markers) who are negative for dysplasia on clinical surveillance histology will also be offered a research endoscopy (funded by the study) In addition to surveillance biopsies (paid for by the study), sponge procedure will be repeated, and research esophageal brushings using a high capacity endoscopic brush (Hobbs Medical) will be obtained for detection of methylated DNA biomarkers of dysplasia.

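### Discrepant resolution, one of three methods listed to correct for missed dysplasia, overstates marker sensitivity if only discordant patients are re-labelled, and the statistical section makes no use of the re-examined double negatives

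*Combined protocol and SAP*

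**What the plan says.** Sample size and Statistical analysis (Phase 2) expects some BE patients with negative surveillance histology to have dysplasia, and says that this will bias the marker's accuracy estimates. It adds "There are several approaches in the literature to address this issue; all with their own caveats", and then "The three approaches that will be investigated are latent class analysis, Bayesian estimation, and discrepant resolution". The sample size was inflated to "correspond with a 30% prevalence of undetected dysplasia in those with no dysplasia on conventional surveillance endoscopy". No method is named as primary, and no estimator is written out.

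Study procedures, section C, supplies the second look. Item viii offers a research endoscopy to discordant patients: "Patients who are biomarker positive (for dysplasia related DNA methylation markers) but negative for dysplasia, as well as those biomarker negative but positive for dysplasia". It gives two purposes, finding missed dysplasia and assessing the panel's sensitivity. Item ix offers the same repeat to some double negatives: "An equal number of biomarker negative (for dysplasia related DNA methylation markers) who are negative for dysplasia on clinical surveillance histology will also be offered". Patients positive on both marker and histology are not re-examined.

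The Statistical analysis section sets the dysplasia cutoff at the 90th percentile in BE patients without dysplasia. It does not say whether that means index histology or a corrected status. Nor does it say how the item ix results enter the accuracy estimates, how those patients are chosen, or which count they are to equal.

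**The concern.** Discrepant resolution, taken in its plain sense, lets the reference status change only in patients whose marker and histology disagree. A marker-positive patient in whom dysplasia is later found moves from false positive to true positive. A marker-negative patient with negative histology stays a true negative whatever the esophagus contains. The reference standard then depends on the test under evaluation.

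Phase 2 aim 2 is the sensitivity and specificity of the panel for dysplasia and carcinoma. A correction meant to remove bias would add bias of its own, in the marker's favour. The general remark that all approaches have caveats does not give the direction of this one.

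**Working it through.** **The plan's own figure.** Table 2 gives 95% half-widths for sensitivity. With 1.96 × √(p(1−p)/n) and n = 65, p = 0.75, 0.80, 0.85 and 0.90 give 0.1053, 0.0972, 0.0868 and 0.0729 (plan: 0.105, 0.097, 0.087, 0.073). With n = 100 the results are 0.0849, 0.0784, 0.0700 and 0.0588 (plan: 0.085, 0.078, 0.070, 0.059). Table 2 reproduces, and I read 65 as the number per dysplasia group (row "N no BE/BE without dys/BE with dys").

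**Notation**
- a: marker-positive, histology-positive
- c: marker-negative, histology-positive
- b1: dysplasia found on repeat in marker-positive, histology-negative patients
- d1: dysplasia hidden in marker-negative, histology-negative patients

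Discrepant-only sensitivity is (a + b1)/(a + b1 + c). True sensitivity is (a + b1)/(a + b1 + c + d1). With correct positive histology and a perfect repeat, the first exceeds the second whenever d1 > 0.

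**Illustration.** From the plan: 65 and 65 patients, 30% missed dysplasia, the sensitivities of Table 2. Assumed: 90% specificity in truly non-dysplastic patients, marker and endoscopy errors independent given true status, no false-positive histology, a perfect repeat, full uptake. Of the 65 histology-negative patients, 65 × 0.30 = 19.5 are dysplastic and 45.5 are not.

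| True sensitivity | a | c | b1 | d1 | Discrepant-only |
|---|---|---|---|---|---|
| 0.75 | 48.75 | 16.25 | 14.625 | 4.875 | 63.375/79.625 = 0.796 |
| 0.80 | 52 | 13 | 15.6 | 3.9 | 67.6/80.6 = 0.839 |
| 0.85 | 55.25 | 9.75 | 16.575 | 2.925 | 71.825/81.575 = 0.880 |
| 0.90 | 58.5 | 6.5 | 17.55 | 1.95 | 76.05/82.55 = 0.921 |

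The excess is 4.6, 3.9, 3.0 and 2.1 points. Over 10% to 40% missed dysplasia it runs from 0.8 to 5.8 points. Specificity also rises slightly: at true sensitivity 0.75 it is 45.825/50.375 = 0.910 against 0.90. Uncorrected index-histology sensitivity in this scenario is 48.75/65 = 0.75, which is right.

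**If the cutoff is set on index-negative patients.** The illustration has 14.625 + 4.55 = 19.2 of 65 histology-negative patients marker-positive (29.5%). A cutoff at the 90th percentile of that group allows only 6.5. Under independence, sensitivity could then not exceed 0.10/0.30 = 0.33, so the table does not apply. Dropping independence, take index sensitivity 0.75 and let all 6.5 be dysplastic:
- discrepant-only: (48.75 + 6.5)/(65 + 6.5) = 55.25/71.5 = 0.773
- pooled truth: 55.25/(65 + 19.5) = 55.25/84.5 = 0.654

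Both are upper limits. If only 3.25 of the 6.5 are dysplastic, they are 0.762 and 0.615. The gap is about 12 points in the first case and 15 in the second, against Table 2's half-width of 0.105. Much of it is already in the index figure (0.75 against 0.654). Discrepant resolution then moves the estimate further from the truth.

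**What the item ix sample can do.** Return to the table at 0.75. There are 45.8 double negatives, 4.875 of them dysplastic. Item ix would re-examine 35.4 of them (77%) if matched to all discordants, or 19.2 (42%) if matched to the marker-positive, histology-negative group.
- Added without weights: 0.760 or 0.776.
- Weighted by the inverse of the sampled fraction: 63.375/(65 + 14.625 + 4.875) = 0.750.

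**An imperfect repeat.** Assume it finds 70% of dysplasia, independently of the marker, and that positive index histology stands. Weighted sensitivity is 58.99/78.65 = 0.75. Weighted specificity is 42.41/51.35 = 0.826 against a true 0.90.

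**The case against.** The design is better than the phrase discrepant resolution suggests. Item ix re-examines the very group that drives the inflation, and nothing says that its results will be discarded. If they enter even without weights, the excess at 30% missed dysplasia is 0.7 to 2.6 points over the Table 2 sensitivities. The method is one of three to be investigated, caveats are acknowledged, and the plan calls itself an initial feasibility study. Under conditional independence, index-histology sensitivity needs no correction.

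These points stand, and they limit the finding. They do not remove it, because collecting the item ix results is not the same as specifying an estimator that uses them.

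Three stronger readings are tempting and unsupported:
- A reader might infer that the study re-examines only patients who disagree with the marker. Item ix shows otherwise.
- A reader might infer that discrepant resolution will supply the main result. Nothing in the text ranks the three methods.
- A reader might add that negative repeats will overturn positive index histology. With an assumed 70% repeat sensitivity, that would turn a true 0.75 into 0.838. The plan states neither that rule nor that sensitivity.

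**Conclusion.** The concern holds in a limited form. Discrepant-only re-labelling overstates sensitivity whenever double negatives hide dysplasia, and the plan's own 30% figure makes that likely. The direction is algebraic if positive histology is correct and the repeat finds the dysplasia present. It also holds in the example with an assumed 70% repeat under independence and no overturning of index positives (0.784 against 0.75).

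The size depends on assumptions the documents do not settle. It is about 2 to 5 points at 30% missed dysplasia under independence, and at least about 12 points from the pooled truth if the cutoff is set on index-negative labels and index sensitivity is 0.75. These are two separate scenarios and should not be combined.

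The gap in the plan is that it lists this method with no stated direction of bias, and leaves unspecified how the item ix data would correct it. A reader might also infer that weighting those data gives an unbiased answer outright. That needs random selection of the item ix patients and uptake unrelated to true status, whereas patients are only offered the procedure.

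**What to change.** 1. Do not use discrepant-only re-labelling to estimate sensitivity or specificity. If it is shown at all, label it descriptive and state its upward bias.
2. Estimate accuracy from index histology plus second-look results in both histology-negative strata, marker-positive and marker-negative. Weight each re-examined patient by the inverse of the fraction of the stratum re-examined.
3. Draw the item ix patients at random from the double negatives, and define which count their number is to equal.
4. In this analysis, do not re-label positive index histology solely because a repeat is negative. The background section describes patchy dysplasia and sampling error, and item iv allows resection at the index endoscopy.
5. Keep the latent class and Bayesian models to address an imperfect second look. They can also examine errors in positive histology, since the background notes poor agreement among pathologists.
6. State that the weighted estimator assumes non-informative uptake, and that it understates specificity if the second look misses dysplasia.
7. Say whether the 90th-percentile cutoff is set on index histology or on corrected status.

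The cost is SAP wording, a sampling rule and a weighted analysis of data already planned. Expect a less favourable sensitivity than discrepant resolution would give, and a somewhat wider interval.

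### Table 2's 65 histology-negative BE patients give 45.5 true non-dysplastic subjects at 30% undetected dysplasia, not the stated 50; 72 are needed on average

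*Combined protocol and SAP*

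**What the plan says.** The text before Table 2, in the Phase 2 part of the section Sample size and Statistical analysis, expects some BE patients with negative surveillance histology to have dysplasia that was missed. It then makes three linked statements:

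- The table is already adjusted: "We have hence inflated the sample size estimates in table 2".
- The adjustment is for a "30% prevalence of undetected dysplasia in those with no dysplasia on conventional surveillance endoscopy".
- Its purpose is "to ensure that we have 50 true BE subjects without dysplasia".

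Table 2 has one row of group sizes, labelled "N no BE/BE without dys/BE with dys". It shows 100 in the four columns for BE against no BE, and 65 in the four columns for BE without dysplasia against BE with dysplasia.

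Two other statements bear on the consequence. The preceding paragraph gives a separate requirement for the multi-marker model, "a minimum of 140 to 210 cases and an equal number of controls is required", and then says "We anticipate enrolling up to 1000 participants". The Statistical analysis section uses the group without dysplasia to set the cut-off: "Marker specificity will be defined as the 90th percentile value in subjects with BE and no dysplasia".

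**The concern.** The plan names the rate, the group the rate applies to, and the number of true negatives it wants. Those three inputs fix the required group size, and it is not 65. The pattern is a familiar slip: the starting number was multiplied by one plus the rate, where a loss expressed as a share of the enrolled group requires division by one minus the rate.

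At stake is the make-up of the reference group for dysplasia. It sets the 90th-percentile cut-off, and the plan itself says that undetected dysplasia in it will bias the accuracy estimates. The expected split between true and false negatives is therefore a planning figure for the latent class, Bayesian and discrepant-resolution analyses. Read literally, Table 2 gives 45.5 and 19.5, not 50 and 15.

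**Working it through.** **Inputs, all from the Phase 2 sample-size text and Table 2**

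- Target: 50 true non-dysplastic BE subjects.
- Undetected dysplasia: 30% of histology-negative BE patients.
- Table 2 group size for the dysplasia comparison: 65.
- Confidence level: 95%.

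**1. Is 65 the number the table was built on?** The half-width is 1.96 × √(s(1 − s)/n).

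| Sensitivity s | n = 100 | Table 2 (BE vs no BE) | n = 65 | Table 2 (dysplasia) |
|---|---|---|---|---|
| 0.75 | 0.085 | 0.085 | 0.105 | 0.105 |
| 0.80 | 0.078 | 0.078 | 0.097 | 0.097 |
| 0.85 | 0.070 | 0.070 | 0.087 | 0.087 |
| 0.90 | 0.059 | 0.059 | 0.073 | 0.073 |

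All eight bands reproduce, so 65 is not a garbled cell. Because these are bands for sensitivity, the match directly confirms the group with dysplasia. That 65 also applies to the group without dysplasia rests on the shared row label.

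**2. Where does 65 come from?** 50 × (1 + 0.30) = 65 exactly.

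**3. What does 65 yield on the stated definition?**

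- True non-dysplastic: 65 × (1 − 0.30) = 45.5.
- Undetected dysplasia: 65 × 0.30 = 19.5.
- Shortfall: 50 − 45.5 = 4.5, and 4.5/50 = 9%.

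**4. What does the target require?** 50/(1 − 0.30) = 71.4, so 72. Check: 72 × 0.70 = 50.4, and 71 × 0.70 = 49.7.

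**5. When would 65 be right?** Only if (65 − 50)/65 = 15/65 = 23.1% had undetected dysplasia.

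**6. How firm is the target?** The calculation above concerns the average. If patients' true states are independent, each non-dysplastic with probability 0.70, the binomial chance of at least 50 true non-dysplastic subjects is:

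| Histology-negative patients | Expected true non-dysplastic | P(at least 50) |
|---|---|---|
| 65 | 45.5 | 0.14 |
| 72 | 50.4 | 0.60 |
| 76 | 53.2 | 0.82 |
| 81 | 56.7 | 0.96 |

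**7. Could the larger enrolment cover the gap?** The 140 to 210 cases are not defined by group, so two readings are shown for illustration.

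- If cases are BE patients and 65 of them have dysplasia (an assumption borrowed from Table 2), then 140 − 65 = 75 to 210 − 65 = 145 are histology-negative. That gives 75 × 0.70 = 52.5 to 145 × 0.70 = 101.5 true non-dysplastic subjects.
- If the controls are BE patients without dysplasia, 140 × 0.70 = 98 to 210 × 0.70 = 147.

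**8. Effect on precision.** The plan sets no precision target for specificity, so this only indicates scale. At 90% specificity, 1.96 × √(0.90 × 0.10/n) is 0.087 at n = 45.5 and 0.083 at n = 50, if true status were known. It is 0.073 if the cut-off rests on all 65 histology-negative patients.

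**The case against.** The strongest reply is that nothing turns on the slip. The multi-marker requirement and the ceiling of 1000 make it unlikely that 65 per group will limit recruitment, and on both readings in step 7 the target of 50 is met on average. No planned calculation uses the 50: the Table 2 bands are for sensitivity, specificity is fixed at 90%, and no stated criterion fails at 45.5. This stands as a limit on the consequence. It does not reconcile the text with the table, because the plan credits the 50 to the inflated Table 2 numbers and nowhere states how many histology-negative BE patients it will enrol. The two readings in step 7 are also only examples; another case mix could give a smaller number.

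A second reply is that the 30% might be meant relative to the 50 true negatives, which would justify 65. The sentence names its denominator as patients with no dysplasia at conventional surveillance endoscopy, so this reading contradicts the text.

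A third reply is that 72 does not guarantee 50 either. That is correct: 72 meets the target only in expectation, and the wording should reflect this.

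**Conclusion.** The concern holds. On the plan's own inputs, 65 histology-negative BE patients are expected to contain 45.5 true non-dysplastic subjects, 4.5 (9%) fewer than stated, and 72 are needed to reach 50 on average. This rests on the 30% applying to histology-negative patients, as the text says, and on the N row giving 65 for the group without dysplasia, as its label says.

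The practical weight is modest. A shortfall arises on average only if fewer than 72 such patients are enrolled. The printed sensitivity bands stand, and the loss of precision at 90% specificity is about 0.4 points (8.7 against 8.3). This is an error in the sample-size justification that should be corrected; it does not threaten the main estimates.

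**What to change.** Amend the sentence before Table 2 in one of these ways:

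- **Restate the yield.** Say that 65 histology-negative BE patients are expected to give about 45 true non-dysplastic subjects at 30% undetected dysplasia. This costs one sentence and no patients.
- **Correct the number.** Set the group without dysplasia at 72 (50/0.70). Split the N row of Table 2 so that the group with dysplasia stays at 65 and the printed bands remain valid. Describe 50 as the expected number, not an assured one. This costs 72 − 65 = 7 more histology-negative BE patients, within the ceiling of 1000. If a firm assurance of at least 50 is wanted, 76 patients give about 80% probability and 81 about 95%, under the independence assumption.
- **Point to the larger enrolment.** If that is what secures the 50, say so here and state the planned number of histology-negative BE patients. This costs one sentence.
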